The research team will call the patients in the evening and explain the purpose of the study and will obtain oral consent. Before calling the patient, the research team will review the EPIC notes to make sure their COVID results are shared and discussed with the patients. Oral consents will serve as a method of patients giving consent for engaging in the study discussion. The paper consents will be delivered to the patients with the study materials (tablet, sensors SPO2, and blood pressure cuff). After reading the consents, patients have the opportunity to decline participation in the study and return the study materials. Once patients sign the consent, patients will have two options to return the signed copy. Either they can take a picture of the signature page and email or text it to the research team, or at the end of the study, they can return the signed consents along with the tablet. We will keep a registry of the consenting process. For patients who email the signature, the investigator portion will be signed and dated on the day of receiving the email. For patients who are returning the signed consent with the tablet package, the investigator portion will be signed and dated on the day of receiving the tablet.

Delivery and Return of the Study Materials

The following day morning, the research staff will drop off the monitoring packages at the patient's preferable drop-off locations. The research team will call the patients to confirm the receiving of the study materials. Once the packet is delivered, the study team will share the details of the patients with ImagineMic, the external company which will be monitoring the patients. Once the patient completes

the 14 days of participation, the patient is required to return the study materials to the study team. The research team will make the necessary arrangements for the return of the study materials.

External Monitoring

ImagineMic will be monitoring the patients for CDC recommended 14 days. (25) ImagineMIC has extensive monitoring experience and is providing services in different capacities and capabilities. (25) ImagineMic uses a secure, HIPPA compliant platform for monitoring the patients. Additionally, round the clock, licensed healthcare professionals continuously monitor these data from a monitoring intervention center. Detailed monitoring plans are explained in the submitted brochure (Appendix-1).

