Monitoring will be prematurely terminated if the patient requires inpatient hospitalization; in all other cases, monitoring will be continued for fourteen days. During the monitoring period, patients will have the opportunity to call and speak to the medical professional at the Monitoring Intervention Center and also can call 911 in case of a severe emergency. Additionally, submitted is the guidelines put together by IMagineMic regarding the treatment and transfer of COVID-19 patients from home to the emergency (Appendix-2)

The patients will be remotely monitored for their vital signs such as blood pressure, heart rate, SPO₂, skin temperature, respiratory rate, two lead ECG, and accelerometer.

All the collected physiologic data will be transmitted to a central monitoring station where it will be evaluated continuously by licensed healthcare workers (MD, RN, and NP) who will provide real-time support to the patients. Also, the research team will obtain all the data points for future analytic purposes. Additionally, the research team will conduct a 30 day follow up phone call to catch information needed in case subjects end up visiting an outside institution.

Control Group

In this study control group will be patients those patients who are COVID positive and discharged from the ER and are not contacted by the study team during the same study period. In order to avoid chronological bias, it is essential to have controls from the same period as in the intervention group. The standard of care, the presentation, and the outcome of the disease are very much different in the surge phase of the COVID when compared to post surge months. Hence it is crucial to avoid chronological bias when comparing intervention and control groups. Additionally, in terms of evaluating the efficacy of the intervention, using patients from the surge period as a control group could potentially impact the conclusion of the study.

Regarding the care given to the control patients, Montefiore Emergency Department has a standard of operating protocols for patients discharged from the emergency room. All the usual standard of care available for the patients discharged from the emergency room will be provided to the patients, including telephone consultations. The study team will not interfere or dictate the care provided to the control patients.

Technology

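### The signed consent may come back only with the tablet after monitoring ends, so forms could be missing more often in admitted monitored patients, and the plan has no rule for them

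*Combined protocol and SAP*

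**What the plan says.** Recruitment Strategy separates two consents. The telephone consent has a narrow scope: "Oral consents will serve as a method of patients giving consent for engaging in the study discussion". Participation rests on a paper form delivered with the equipment, and patients may still decline after reading it. The signed copy can come back in two ways. The early route is "Either they can take a picture of the signature page and email or text it to the research team", with no deadline. The late route is that "at the end of the study, they can return the signed consents along with the tablet", and then "the investigator portion will be signed and dated on the day of receiving the tablet". The same section adds "We will keep a registry of the consenting process", without giving its contents or a rule for forms that never arrive.

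Delivery and Return of the Study Materials sets the trigger for monitoring: "Once the packet is delivered, the study team will share the details of the patients with ImagineMic". Receipt of a signed form is not a condition. Return of the kit is described for completers: after finishing "the 14 days of participation, the patient is required to return the study materials to the study team". The team undertakes to arrange the return.

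External Monitoring states "Monitoring will be prematurely terminated if the patient requires inpatient hospitalization". Under Objectives, inpatient admission is the primary comparison. Under Control Group, controls are not contacted by the study team. Statistical Analysis defines no analysis population and does not mention unreturned forms.

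**The concern.** On the late route, consent is documented only after participation is over. The step that produces the document, return of the kit, is described for patients who complete 14 days. A patient who reaches the primary event leaves that path: monitoring stops, the patient is in hospital, and no return procedure is written for that case or for death. Whether a signed form is on file may therefore depend on the outcome, and only in the monitored group.

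This matters if patients without a form on file are left out of the analysis. Removing admitted patients from one group lowers that group's admission rate and imitates the benefit that the study is looking for. Because no rule is written, the team would have to decide how to handle these patients once their outcomes are known.

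**Working it through.** **Inputs from the plan (Statistical Analysis):** 150 per group; 15% admission without monitoring; a reduction of 10%, read as 15% to 5%; 80% power; chi-square test; two-sided P < 0.05.

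**The plan's own figure.** The usual two-proportion formula for 15% against 5% gives 141 per group without continuity correction and 160 with it. At 150 per group the power is 82.6%. The stated 150 is not matched exactly, but it exceeds the uncorrected requirement. Nothing below depends on it.

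**Assumptions not in the plan:** patients without a form on file are excluded; a share L_a of admitted and L_n of non-admitted monitored patients is lost this way; no control is lost; the true rate is p = 15% in both groups. The documents give neither a loss rate nor the share of patients who would use the late route.

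**Apparent monitored rate** = p(1 − L_a) / [p(1 − L_a) + (1 − p)(1 − L_n)].

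Example with L_a = 20%, L_n = 0: 0.15 × 0.80 = 0.120, and 0.120 / (0.120 + 0.850) = 12.4%.

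The chance of a false significant benefit is the share of simulated trials with no true effect in which the uncorrected chi-square test gives P < 0.05 in favour of monitoring (200,000 or more runs per row).

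| Loss, admitted | Loss, non-admitted | Apparent monitored rate | False benefit |
|---|---|---|---|
| 0% | 0% | 15.0% | about 2.5% |
| 10% | 0% | 13.7% | 5.0% |
| 20% | 0% | 12.4% | 9.6% |
| 30% | 0% | 11.0% | 17% |
| 20% | 10% | 13.6% | about 5% |
| 30% | 20% | 13.4% | 5.5% |
| equal | equal | 15.0% | about 2.5% |

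The bias is driven by the difference in loss between admitted and non-admitted patients. Loss as such does not produce it.

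**Two checks on scale.**
- L_a applies to all admitted monitored patients. If half of them used the photo route and lost nothing, L_a = 30% would need 0.30 / 0.50 = 60% of late-route admitted patients to have no form.
- Start from 22 of 150 admitted in each group (14.7%). Removing 11 admitted monitored patients leaves 11/139 = 7.9%, z = 1.80. Removing 12 leaves 10/138 = 7.2%, z = 2.00. From exact equality, 12 of 22 would have to go before the result became nominally significant.

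**At the planned effect.** With a true monitored rate of 5% (7.5 expected admissions), L_a = 20% and L_n = 0, the apparent rate is 0.040 / (0.040 + 0.950) = 4.0%. The shift is one percentage point.

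**The case against.** A reader might infer that admitted patients would have no valid consent and would drop out of the monitored group. The documents do not support either step. Signing is described as coming before return, so a form that never arrives means no signed copy on file; the patient may well have signed at home. No passage excludes a patient whose form is not back. Whether such data could be used is a matter for the IRB that the documents leave open.

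The plan also has partial safeguards. The photo route is offered, and patients must be able to handle a tablet to be eligible, so that route is feasible. The team confirms receipt of the kit by telephone, arranges its return, keeps a consent registry and makes a 30-day call. Kit return after a death does not rest on the patient alone. Finally, the larger error rates above require zero loss among non-admitted patients.

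All of this stands, and it limits the claim to a conditional one. It does not remove the gap. The photo is optional and has no deadline, the registry has no rule for missing forms, the return arrangements name no procedure for admitted or deceased patients, and the 30-day call is there to collect outcomes.

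A further objection concerns the remedy. A photo gate applied to the monitored group alone would drop anyone admitted before sending the photo, which moves the same problem earlier. That is correct, and the fix below allows for it.

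**Conclusion.** The concern holds in conditional form. The plan permits documentation of participation consent to wait until the kit returns, shares details without it, describes kit return for completers only, and gives no rule for forms that do not arrive. Missing forms could therefore be related to the primary outcome in one group only. That admitted patients are more likely to lack a form is plausible, but no figure in the documents shows it.

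If such patients were excluded and loss were greater among the admitted, the bias would favour monitoring. With a true rate of 15% in both groups, the chance of a false benefit runs from about 5% (a 10-point difference in loss) to about 17% (30% of admitted against none of the non-admitted), compared with a nominal 2.5%. With equal loss, or if nobody is excluded, there is no bias from this source. The change is worth making because it is cheap and the plan already offers the better route.

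**What to change.** 1. Require the signature page by photo, text or e-mail before the patient's details go to the monitoring company and before the patient counts as enrolled. Delete return with the tablet as the sole route of documentation.
2. State that every patient enrolled this way stays in the monitored group for all endpoints, whether or not the kit comes back.
3. Count admissions in both groups from a matching start point after emergency-room discharge, for example by requiring controls to be free of admission up to the corresponding time. Without this, the consent gate would itself remove early admissions from the monitored group only.
4. Report how many patients received a packet but were admitted, or declined, before sending the form.

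The cost is protocol wording, a check in the registry that is already kept, and a start-date rule for controls. A few patients may not send the photo, or may start slightly later.

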The central hypothesis motivating this study is that remote patient monitoring (RPM) of infectious disease patients can efficiently facilitate self-isolation. Additionally, RPM can assist in more rapid identification of patients at risk, facilitate detection of patient deterioration, and enable early interventions, all of which play a vital role in resource utilization and outcomes.

Specific Aims

Aim-I **To develop and test a clinical care pathway that can be utilized in similar epidemic conditions in the future**. To study this aim, we will be using the COVID-19 medical surge as a condition to evaluate the framework of delivering care through remote patient monitoring. The success of this care delivery model will be evaluated on ease of model implementation, patient satisfaction, clinical outcomes, and the utilization of shared decision making.

Aim-II **To evaluate remote patient monitoring for appropriate resource utilization in epidemic and pandemic conditions**. To evaluate this aim, we plan to compare the emergency department (ED) visits and inpatient admission of patients with and without wearable remote patient monitoring devices. Additionally, we will compare the number of patients that required critical interventions (mechanical ventilation and ECMO) during the hospital stay.

Aim III **To evaluate the utilization of wearable technology for upfront predictions of patients that would require inpatient admissions.** To evaluate this aim, patients who are diagnosed with COVID-19 and are undergoing self-quarantine will be closely monitored using a wearable device, and sharedclinical decisions will be made based on the monitored data and patient diary. The comparison group will be patients undergoing routine standard of care at the hospital. ED visits, inpatient hospital admissions, and patient satisfaction will be the outcome measures compared between the two groups.

Aim IV To evaluate the association between early identification of critical, abnormal vital signs and the prevention of serious adverse events. To evaluate this aim, patients in the monitored group and non-monitored group will be compared for ED visits, inpatient admissions, length of hospital stay, and serious adverse events.

Objectives

The primary purpose of the study is to compare the number of inpatient admissions between the monitored and non-monitored patients.

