The secondary endpoints are to compare the number of ED visits, length of stay, patient satisfaction, the incidence of mechanical ventilation, ECMO, and serious adverse events (events requiring extended hospital stay).

Methods

In this prospective observational study, we are planning to recruit COVID-19 positive patients visiting emergency rooms (ER) associated with Montefiore Medical Center

Inclusion Criteria

- Diagnosis of COVID-19 (first-time COVID-19 diagnosis)
- Able to read and understand English

- Able to navigate and fulfill tasks on an electronic tablet
- 21 years and older
- Patients that do not require an inpatient admission as per the treating physician
- Patients who are insured through Medicare
- Patients who are staying in the same household for at least 15 days

Exclusion Criteria

- Have never used a mobile phone or tablet in the past
- Patients with an implanted pacemaker
- Patients with a diagnosis of hyperhidrosis
- Acute allergic reactions to the patches
- Confirmed diagnosis of psychiatric illness or anxiety disorder
- All private insurance patients

Recruitment Strategy

Every day around 4 pm, the research team will generate a list of patients who were tested COVID-19 positive and are discharged from ER without requiring inpatient admission. This list will include all the COVID-19 positive patients from all the emergency departments associated with Montefiore Medical Center. The potential patient list will be generated on every alternate day; for example, the list will be generated on (Monday, Wednesday, and Friday). We are only planning to enroll 5-6 patients on a single day. Alternate day enrollment will potentially allow us to have a balance in the number of patients in the intervention and the control group. Also, it helps us to streamline the study logistics. After screening for inclusion and exclusion criteria, the research team will identify potential patients eligible for the study.

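### Inpatient admissions have no start or counting window common to both groups, and the entry steps can drop early admissions from the monitored group only

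*Combined protocol and SAP*

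**What the plan says.** All references are to the combined protocol and SAP.

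- **Objectives.** "The primary purpose of the study is to compare the number of inpatient admissions between the monitored and non-monitored patients". Neither a start date nor a number of days is attached. Statistical Analysis assumes 15% admission in controls and a 10% reduction, also without a period, and names a chi-square test for categorical outcomes.
- **Recruitment Strategy.** Patients are taken from a list made at about 4 pm. The section first describes the list as daily, then says: "The potential patient list will be generated on every alternate day". It gives balance between the group sizes as one reason for alternate-day enrolment, and adds a cap: "We are only planning to enroll 5-6 patients on a single day". Contact comes next: "The research team will call the patients in the evening and explain the purpose of the study and will obtain oral consent". Written consent follows delivery, with a way out: "After reading the consents, patients have the opportunity to decline participation in the study and return the study materials". One dating rule, "the investigator portion will be signed and dated on the day of receiving the tablet", applies to those who send the form back with the equipment.
- **Delivery and Return of the Study Materials.** The kit comes after the call: "The following day morning, the research staff will drop off the monitoring packages". Monitoring is handed over only then: "Once the packet is delivered, the study team will share the details of the patients with ImagineMic". Participation lasts 14 days.
- **External Monitoring.** Monitoring lasts 14 days and ends early on hospitalization. A follow-up call at 30 days is meant to pick up visits elsewhere. It is described with the monitored patients, and its day 0 is not given.
- **Control Group.** Controls are COVID-positive patients sent home from the emergency room in the same study period whom the study team did not approach. No start of follow-up is given for them.

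**The concern.** For monitored patients a start at delivery and a 14-day period can be inferred. For controls there is no start at all, and neither the 14 days nor the 30-day call is tied to the endpoint. The investigator's consent date cannot serve as day 0, because for some patients it is the day the tablet comes back.

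The two groups also enter differently. To become a monitored patient, someone must in practice stay out of hospital through the evening call and the next morning's delivery. Controls face no such condition. A patient admitted in that interval is likely to drop out of the monitored group, while the same event in a control can count. If control admissions are counted from discharge, the primary comparison tilts towards monitoring with no true effect. A patient listed on an enrolment day but admitted before the call also meets the written definition of a control, unless controls come only from off-days.

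The same-period rule deals with calendar time, not with the start of each patient's follow-up, and a chi-square test does not correct for it. With no rule written down, the start and window could be chosen after the data are seen.

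**Working it through.** **The plan's own figure.** Inputs from Statistical Analysis: 15% in controls, a 10-point reduction (so 5% monitored), 80% power, two-sided 0.05. The pooled normal formula is n = [1.96 × √(2 × 0.10 × 0.90) + 0.842 × √(0.15 × 0.85 + 0.05 × 0.95)]² / 0.10² = 140.1, so 141 per group. The plan's 150 is not reproduced exactly but exceeds this. Power at 150 per group is 82.6% by the normal formula and 84.3% by exact enumeration of the uncorrected chi-square test. The sample size is not the issue here.

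**Assumptions, since the documents give no admission timing.** No true effect; 15% control risk over 14 days; 150 analysed per group; lag g = 0.75 day from a 4 pm list to a delivery taken as 10 am next day (18/24). The documents say only morning. Patients admitted during the lag leave the monitored group only. With no bias (15% v 15%), exact two-sided error is 4.9%, of which 2.5% favours monitoring.

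**Evenly spread admissions, both groups counted to the same end.**
- Admitted during the lag: e = 0.15 × 0.75/14 = 0.0080.
- Monitored rate: (0.15 − 0.0080)/(1 − 0.0080) = 14.31%.
- Spurious benefit: 0.69 point. Two-sided error 5.2%; rejection favouring monitoring 3.6%.

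**Early clustering, equal 14-day windows from each group's own start.** F(t) = c(1 − exp(−t/5)) with F(14) = 0.15, so c = 0.1597.
- F(0.75) = 0.0222 and F(14.75) = 0.1514.
- Monitored rate: (0.1514 − 0.0222)/(1 − 0.0222) = 13.20%.
- Spurious benefit: 1.80 points. Two-sided error 7.2%; rejection favouring monitoring 6.4%.
- To separate clustering from the window rule, count both groups to the same end instead: (0.15 − 0.0222)/(1 − 0.0222) = 13.07%, or 1.9 points. Clustering, not the window rule, drives the increase.

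**Cases that remove or reverse it.** With equal windows and a constant hazard the bias is 0. With equal windows and rising risk (Weibull shape 1.5) it is −0.7, −1.2 or −2.3 points for lags of 0.5, 1 or 2 days. Separately, if 5%, 10% or 20% of control admissions are at outside hospitals and are missed because only monitored patients get the 30-day call, the control rate falls by 0.75, 1.5 or 3.0 points (0.15 × share). That works against monitoring.

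**Power with a common index time.** If a share s of the 15% precedes it, the control rate is (0.15 − 0.15s)/(1 − 0.15s) and the monitored rate is one third of that.
- s = 10%: 13.7% v 4.6%, exact power 80.3%.
- s = 20%: 12.4% v 4.1%, 75.4%.
- s = 30%: 11.0% v 3.7%, 69.6%.

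**The case against.** The strongest defence is that the plan is less silent than it looks. Handover at delivery, a 14-day period and termination on hospitalization together imply a start, a length and an ending event for monitored patients. That stands, and it narrows the gap to the controls' start and to the missing link between the endpoint and either 14 or 30 days.

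Second, giving group balance as a reason for alternate-day enrolment suggests that controls come at least partly from off-days. If they come only from off-days, a patient admitted before the call is not moved into the control group. This also stands as a possibility, but the daily cap could equally leave listed patients uncontacted, and the Control Group section does not say which applies. On either reading the patient is still lost from the monitored group.

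Third, the lag described from listing is under a day, and even spread then gives an error rate barely above nominal. That is correct. A longer lag from discharge is possible if a list also covers off-day discharges, but the text does not say so.

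Fourth, being reached by phone and agreeing to take part is volunteer selection, not a timing problem, and a common index time leaves it in place. That is also correct.

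**Conclusion.** The point holds in a limited form. The primary endpoint lacks a start and window common to both groups, and the entry rules as written can remove early admissions from the monitored group only. Nothing in the visible text prevents this.

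The size is not fixed by the documents. On the assumptions above it is about 0.7 point with even spread and about 1.8 points with early clustering, against a 10-point target. Much larger values need a longer lag or stronger clustering.

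A reader might infer three stronger things that the documents do not support:
- **That a favourable result would probably be an artefact.** A false-benefit rate near 20% needs a 2-day lag together with the assumed 5-day time constant, and neither is stated.
- **That the bias must favour monitoring.** The direction depends on how admissions are counted and on the shape of the risk. Missed outside admissions of controls could offset or reverse it.
- **That one group is counted to day 14 and the other to day 30.** With a constant hazard and 15% by day 30, this would create about 7.7 points (15% − [1 − 0.85^(14/30)] = 15% − 7.3%). No passage says it will be done.

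This should be corrected because the remedy is cheap and the endpoint is primary. Confidence is medium, because the magnitude rests on assumed timing.

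**What to change.** - Set one index time for both groups: the morning after the 4 pm list that names the patient or, for an off-day control, would have named them.
- Exclude from both groups anyone known to have been admitted or to have died before it, and report these exclusions by group.
- Count admissions over one stated length from that time. Use the same record source in both groups for the primary analysis, and report admissions known only from the 30-day call separately.
- Do not place patients who were contacted and declined (including after delivery), or who were admitted before delivery, in the control group. Report them separately.
- State whether controls come from the same lists or from off-days and which discharges each list covers, and reconcile the daily list with the alternate-day list.
- Apply to controls those eligibility criteria that the medical record can show. Tablet ability and household stay may not be knowable for patients who are never contacted.

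**Cost.** No new visits, but early admissions leave the comparison. With a two-thirds relative reduction and 150 per group, exact power falls from 84% to about 80%, 75% or 70% if 10%, 20% or 30% of admissions precede the index time. The shares are assumed, so power should be given as that range. Holding 80% would take about 149, 166 or 188 per group. Early control admissions or deaths elsewhere may be missed, so the exclusion may be incomplete in that group.

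The alternative is to count both groups from discharge by intended approach. It keeps every admission but costs more power: 74%, 61% or 48% for the same shares, if monitoring acts only after delivery and nobody declines. Selection through being reached and consenting needs its own remedy.

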This study will be integrating two technologies; an FDA approved proprietary body patch and a digital monitoring platform. The FDA approved body patch that will be used in this study is lifesignal biosensor 1AX*, which is capable of monitoring vital signs, including blood pressure, heart rate, temperature, respiratory rate. (26) These patches are also capable of generating electrocardiogram (ECG) and function

as an accelerometer. Additionally, an FDA approved pulse oximeter, and blood pressure monitor will be used to measure the peripheral oxygen saturation and blood pressure, respectively

The digital monitoring platform ImagineMic will be utilized for continuous digital monitoring of the physiologic measurements. (27) The vital signs generated through the biosensor patch will be continuously supervised at the Monitoring Intervention Center (MIC) by licensed healthcare professionals. These data points are monitored 24/7and alerts will be provided to patients in case an intervention is needed. Additionally, based on the condition of the patient, the monitoring staff will facilitate ambulance support if required. The schematic representation of the study proposal is depicted in figure 1.

In addition to remote monitoring, the monitoring team will collect the data about their daily clinical symptoms, including cough, myalgia, difficulty in breathing, and any other clinically significant symptoms. Additionally, at the end of the monitoring period (14days), a personal well-being questionnaire will be administered to those patients who experience no adverse events.

Cost and Reimbursement

There will be no cost for the patient to participate in this study. The department of the anesthesiology (grant fund) and ImagineMic (company monitoring the patients) will share the cost of the wearables. The cost of the monitoring will be billed to the insurance company by ImagineMic. Patients will not be reimbursed for participating in the study.

Data Collection and Storage

All the study data will be collected on a paper case report form (CRF), which will be entered into the computer database. All the data points will be collected and managed using RedCap electronic data capture tools. All the electronic files will be saved in a password-protected computer in the research office. Additionally, de-identified continuous monitoring data will be shared with the Montefiore Center for Health and Data Innovation team for additional analysis.

DSMB

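### The text does not say who receives the 30-day call about outside hospitals, and sets no common source, start date or window for admissions, the primary outcome

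*Combined protocol and SAP*

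**What the plan says.** The Objectives section sets the primary purpose: to "compare the number of inpatient admissions between the monitored and non-monitored patients". It gives no start date, time window or data source. The Statistical Analysis section gives a 15% control admission rate, again without window or source. Data Collection and Storage describes a paper form and a database but does not say where admission data come from.

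The only provision for care elsewhere is the last sentence of External Monitoring: the research team "will conduct a 30 day follow up phone call to catch information needed in case subjects end up visiting an outside institution". That section otherwise describes monitored patients, for whom, unless they are hospitalised, "in all other cases, monitoring will be continued for fourteen days". The Control Group section, which follows directly, describes controls as patients who "are not contacted by the study team during the same study period".

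Two other places bear on the reading. Aim III says that "ED visits, inpatient hospital admissions, and patient satisfaction will be the outcome measures compared between the two groups", and the secondary endpoints include "length of stay, patient satisfaction, the incidence of mechanical ventilation, ECMO, and serious adverse events". The Technology section says "The schematic representation of the study proposal is depicted in figure 1"; that figure and Appendices 1 and 2 were not available to this review.

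**The concern.** By adding the call, the protocol recognises that some patients will go to hospitals outside its own system. If the call reaches one group only and its reports are counted, an outside admission is an event in a monitored patient and is invisible in a control. The hypothesised benefit is fewer admissions under monitoring, so the error works against the intervention: a real benefit shrinks, and no benefit can look like harm. The planned chi-square test is unadjusted and cannot correct for unequal capture. The Control Group section takes care to draw controls from the same period; equal outcome capture needs the same care.

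Separately, two analysts could build different primary datasets from this text, because it does not settle the source, the day counting starts, the day it stops, or whether call reports count. The hospital-based secondary outcomes (ED visits, length of stay, ventilation, ECMO, serious adverse events) share the gap.

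**Working it through.** **Inputs from the Statistical Analysis section.** 150 per group; 15% admitted in controls; a 10% reduction; 80% power; chi-square test, two-sided 0.05.

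**The plan's own figure.** Reading the reduction as absolute (15% to 5%), the pooled normal formula is

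n = [1.960·√(2·0.10·0.90) + 0.842·√(0.15·0.85 + 0.05·0.95)]² / 0.10² = 140.1, so 141 per group.

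That is consistent with 150. A relative reduction (15% to 13.5%) would need 8,525 per group, so the absolute reading is used. Exact binomial enumeration of the uncorrected chi-square test at 150 per group gives power 84.3%. With 15% in both groups, the chance of a significant result in one given direction is 2.5%.

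**Assumptions not in the documents.** s is the share of admissions that occur outside Montefiore, the same in both groups. Only monitored patients are called, all respond, and their reports are counted. For the no-effect rows the groups are taken as comparable, although the study is not randomised. The documents do not say whether 15% and 5% are rates at all hospitals or at Montefiore only, so both are shown. With p the planned monitored rate (0.05 for power, 0.15 for no effect):

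- All-hospital: observed control rate 0.15(1 − s); observed monitored rate p.
- In-system: observed control rate 0.15; observed monitored rate p/(1 − s).

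Example at s = 20%, all-hospital: the control rate is 0.15 × 0.80 = 12%, so the difference shrinks from 10 to 7 points. With no effect, monitoring looks 3 points worse (15% against 12%). In-system: the monitored rate is 0.05/0.80 = 6.25%, so the difference is 8.75 points.

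| Outside share s | 0% | 5% | 10% | 20% | 30% |
|---|---|---|---|---|---|
| Power, all-hospital | 84% | 79% | 74% | 59% | 43% |
| Power, in-system | 84% | 82% | 79% | 71% | 59% |
| False harm with no effect, all-hospital | 2.5% | 3.7% | 5.5% | 11.3% | 21.3% |
| False harm with no effect, in-system | 2.5% | 3.8% | 5.8% | 13.7% | 30.4% |

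If only 60% respond to the call, the monitored rate is multiplied by (1 − 0.4s) and the effect is milder. At 10/20/30% outside, power is 76/65/52% (all-hospital) or 81/77/70% (in-system), and false harm is 4.1/6.7/10.7% or 4.2/7.6/14.2%.

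**The same record query in both groups.** Under the all-hospital reading both rates are multiplied by (1 − s), and power is 82/80/74/67% at 5/10/20/30% outside. Under the in-system reading it stays 84%. In each case this is higher than with monitored-only calls at full response.

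**The same call in both groups.** At an assumed 60% response and 10/20/30% outside, power is 83/81/79% (all-hospital) or 87/90/92% (in-system).

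**Unequal outside shares with records only.** With no true effect and all-hospital rates, 20% outside in monitored patients against 10% in controls compares 12% with 13.5% and gives a false-benefit rate of 5.8%; 30% against 10% compares 10.5% with 13.5% and gives 12.2%.

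**The case against.** The text does not establish unequal capture. The word subjects is undefined. The definition of controls as not contacted may mean only that they were not approached for enrollment. The non-monitored 150 are counted in the enrollment target, and comparing patient satisfaction between groups suggests, without proving, some contact with controls. Figure 1 or the appendices might settle the matter. The bias also needs call reports to enter the primary count, which the purpose of the call makes plausible but no sentence states. All of this stands, and it is why the point is conditional.

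The sizes rest on an outside share that the documents do not give. At 5% the effect is modest (power 79%, false harm 3.7% on the all-hospital reading). That stands too.

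A reader might infer that the missing window biases the comparison whatever was intended, for example with monitored patients counted to day 14 and controls to day 30. The documents do not support this. Fourteen days is the length of monitoring, not an outcome window, and no section assigns the groups different windows. If both are counted over the same period, no window bias arises and the gap is one of specification only.

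Finally, removing outside admissions from the primary count is a choice with a cost. Calling both groups would keep more power on both readings, but it needs contact with controls.

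**Conclusion.** The concern holds in conditional form and should be fixed; confidence is medium. No available section gives one source, start date and window for the primary outcome in both groups, and the most natural reading of the two adjoining sections is that only monitored patients are called. If that is so and call reports are counted, the comparison is biased against monitoring. Over an assumed outside share of 5% to 30% with full response, power falls from 84% to between 79% and 43% (all-hospital rates) or between 82% and 59% (in-system rates). With no true effect, false harm rises from 2.5% to between 3.7% and 21.3%, or between 3.8% and 30.4%. If both groups are called alike, or call reports stay out of the primary count and the outside share is equal, this bias does not arise.

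A reader might go further and conclude that the plan definitely follows up only one group, or that its results will be biased. The text leaves both open. A window bias would arise only if the groups were counted over different lengths of time, which the text neither states nor rules out. The sample size itself is not in error on this point.

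**What to change.** In Objectives, External Monitoring, Control Group and Statistical Analysis:

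- Define the primary outcome as at least one inpatient admission within one stated window (for example 30 days) from ER discharge, found by the same Montefiore record query in both groups.
- State who receives the 30-day call, and reconcile this with the definition of controls.
- If only monitored patients are called, keep call-reported outside admissions out of the primary count. Report them in a sensitivity analysis that varies the outside share by group (for example 0–30% each) and shows where the conclusion changes.
- Apply the same source and window to the hospital-based secondary outcomes.

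The cost is wording and one query run the same way for both groups. It looks feasible because recruitment starts from Montefiore's own emergency departments: "This list will include all the COVID-19 positive patients from all the emergency departments associated with Montefiore Medical Center". Permission to query control records is not stated and must be checked. Outside admissions leave the primary count, which lowers power if the planned rates are all-hospital, and bias remains if the outside share differs between groups; hence the sensitivity analysis.

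Calling both groups with the same script and window is an alternative that keeps more power. It needs contact with controls and a changed control definition, so it is an option rather than the main fix.
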